## **9.5 Exploratory Efficacy Analyses**

For variables with a continuous response range, analyses will be performed similarly to that used for the primary analysis, with focus again on the pairwise contrasts of each dose group to placebo. Baseline in the primary MMRM model will be replaced with corresponding endpoint baseline. Note that the stratification of number of migraine days during the screening/baseline period (4 to  $< 8$  and  $\geq 8$ ) will be included in the additional efficacy analyses if baseline values other than monthly migraine days are included in the corresponding models. There is only one post-baseline assessment for MIDAS and PHQ-9, and thus ANCOVA model will be used to analyze MIDAS and PHQ-9 related endpoints with model terms including treatment group, region, the stratification of

number of classes of failed prior prophylactic treatments (2 and >2), number of migraine days during the screening/baseline period (4 to < 8 and  $\geq$  8) and corresponding baseline score. For the endpoints change from baseline in HIT-6, MSQ 2.1 and EQ-5D-5L descriptive system index score and vas score, Week 16 (follow up visit) will not be included in MMRM model fitting. Only descriptive statistics for Week 16 will be provided.

For variables where the data are essentially binary, comparisons between treatment groups will be done using a generalized linear mixed model for variables with multiple postbaseline assessments. A generalized linear mixed model will assume a binary distribution for the response and uses a logit link. The analysis model will include treatment group, visit, region, number of classes of failed prior prophylactic treatments (2 and >2), and treatment group-by-visit interaction as categorical fixed effects; baseline value and baseline-by-visit interaction will be included as covariates. If baseline values other than monthly migraine days is included in the model, then number of migraine days during the screening/baseline period (4 to < 8 and  $\geq$  8) will also be included in the corresponding analysis. Participants will be included as random effects with unstructured covariance matrix in the model to account for the correlation among repeated measurements. If the model does not converge, then the Toeplitz covariance structure will be used. If the model with the Toeplitz covariance structure does not converge, then the compound symmetry covariance structure will be used. The analysis will be performed based on all postbaseline values using only the observed cases without imputation of missing values. As there is no baseline assessment for the endpoint patient's satisfaction with study medication, baseline monthly migraine days will be included in the model.

For binary endpoints with only one postbaseline assessment (for example, PGIC responder) or responders across 12-week double-blind treatment period, a logistic regression model will be used to model the probability of a response or event with model terms including treatment group, region, number of classes of failed prior prophylactic treatments (2 and >2), and corresponding baseline. If baseline values other than monthly

migraine days is included in the model, then number of migraine days during the screening/baseline period (4 to < 8 and  $\geq 8$ ) will also be included in the corresponding analysis. As there is no baseline assessment for PGIC, baseline monthly migraine days will be used in the logistic regression model as a covariate for PGIC responder analyses.

Plots of fitted (least squares) mean changes and their standard errors for monthly migraine days, monthly headache days and monthly acute medication use days from the MMRM will be presented by treatment group and 4-week interval.

Plots of achievement of  $\geq 25\%$ ,  $\geq 30\%$ ,  $\geq 50\%$ ,  $\geq 75\%$ , and 100% improvement (decrease) in monthly migraine days will be presented by treatment group and 4-week interval, respectively.

In addition, cumulative distribution graph of percent improvement (decrease) in mean monthly migraine days across 12-week treatment period will be provided by treatment group.

## 9.6 Efficacy Subgroup Analyses

Subgroup analyses for primary efficacy endpoint will be performed based on the following subpopulations:

- Region: North America and Europe
- Participants who had baseline migraine days: 4 to < 8 and  $\geq 8$
- Participants who have failed 2 classes of prior oral prophylactic treatments
- Participants who have failed  $\geq 3$  classes of prior oral prophylactic treatments
- Participants who have failed 3 classes of prior oral prophylactic treatments

The same model as that of the primary MMRM model in primary efficacy analysis in Section 9.3.2 will be utilized based on mITT population in support of submission in the US and on the Off-treatment Hypothetical Estimand Population in support of European submissions. For each subgroup analysis, treatment effect and treatment comparison will

be estimated by the LS Means and their difference in LS Means, along with their SE and 95% confidence intervals (CIs).

## **10.0 Safety Analyses**

### **10.1 General Considerations**

Safety data will be summarized for the Safety Population. Safety summaries will be presented by treatment group. For the safety analysis, participants are assigned to a treatment group based on the treatment actually received, regardless of the treatment randomized.

A participant's actual treatment will be determined by the most frequent dose regimen received.

The safety parameters will include adverse events (AEs), clinical laboratory, vital sign, electrocardiographic (ECG), and C-SSRS. For clinical laboratory, vital sign, and ECG, the last non-missing safety assessment before the first dose of treatment will be used as the baseline for all analyses of that safety parameter. Continuous variables will be summarized by number of participants and mean, SD, median, Q1, Q3, minimum, and maximum values. Categorical variables will be summarized by number and percentage of participants.

### **10.2 Adverse Events**

Adverse events (AEs) will be summarized and presented using primary MedDRA System Organ Class (SOCs) and preferred terms (PTs) according to the version of MedDRA coding dictionary used for the study at the time of database lock. The actual version of the MedDRA coding dictionary used will be noted in the AE tables and in the clinical study report. Specific adverse events will be counted once for each participant for calculating percentages, unless stated otherwise. In addition, if the same adverse event occurs multiple times within a participant, the highest severity and level of relationship to investigational product will be reported. Only AEs captured in Study 3101-304-002 will

be considered for TEAEs in this study. For participants rolling over into Study 3101-312-002 (extension study), AEs captured in the extension study will be summarized in the extension Study 3101-312-002 although some AEs might occur within 30 days after the last dose from Study 3101-304-002.

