9.4.2.1. Adverse Events

An AE will be considered a TEAE if the AE began or worsened (increased in severity or became serious) on or after the date (and time, if known) of the first dose of study intervention. TEAEs will be analyzed after treatment start on day 1 through the end of the study. An AE that occurs more than 30 days after the last dose of double-blind study treatment or Visit 8 whichever comes later will not be counted as a TEAE.

An AE will be considered a TESAE if it is a TEAE that additionally meets any SAE criterion.

MedDRA nomenclature will be used to code AEs.

The number and percentage of participants with TEAEs in each study intervention group will be tabulated by system organ class and preferred term and by system organ class, preferred term, and severity.

The number and percentage of participants with treatment related TEAEs in each study intervention group will be tabulated by system organ class and preferred term.

If more than 1 AE is coded to the same preferred term for the same participant, the participant will be counted only once for that preferred term using the most severe and most related occurrence for the summarizations by severity and by relationship to study intervention.

AEs will also be summarized separately for the double-blind treatment and safety follow up phases of the study.

Summary tables will be provided for participants with TESAEs and participants with TEAEs leading to discontinuation if 5 or more participants reported such events. Listings of all AEs, SAEs, and AEs leading to discontinuation by participant will be presented.

The definitions of an AE and SAE can be found in Section 10.3 (Appendix 3).

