## 2.2 Study Design Overview

This is a global, multicenter, randomized, double-blind, placebo-controlled, parallel-group study planned to be conducted at approximately 125 sites globally (North America, Europe, and Asia/Pacific).

[figure not shown]
Participation will begin with a 4-week screening/baseline period. Participants who complete the 4-week screening/baseline period and meet all entry criteria will be randomized to the double-blind treatment period of the study at Visit 2 (Randomization Visit). The double-blind treatment period will last 12 weeks, with a subsequent safety follow-up period of 4 additional weeks. Total duration of study participation for one participant is approximately 20 weeks.

There will be 8 scheduled clinic visits: Visit 1 (Screening/Baseline Visit), Visit 2 (Randomization Visit), Visit 3 (Week 2), Visit 4 (Week 4), Visit 5 (Week 6), Visit 6 (Week 8), Visit 7/ET (Week 12), and Visit 8 (Week 16/EOS/Follow-up). The Visit 8/EOS/follow-up period must be completed for all participants who take at least one dose of study intervention, except for participants rolling over into Study 3101-312-002 (long-term safety extension study). For these rollover participants Visit 8 is not required, because the final Follow-up Visit will be performed at the end of the long-term safety extension study. For participants who screen fail for the long-term safety extension study, the Follow-up Visit of Study 3101-304-002 must be completed.

Per study design (Protocol Sections 10.8.4 and 10.8.5), eDiary data will be collected for participants who early terminated from the double-blind treatment period during the 4 weeks between V7 (Early termination visit) and V8 (Follow-up Visit).

The schematic of the study is shown in [Figure 1](#).

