### **10.2.1 Treatment-Emergent Adverse Events**

Treatment-emergent AEs are defined as any AE with the onset that is after the first dose of study drug. Events when the onset date is the same as the study drug start date are assumed to be treatment-emergent. An AE that occurs more than 30 days after the last dose of double-blind study treatment or Visit 8 whichever comes later will not be counted as a TEAE. All treatment-emergent AEs will be summarized overall, as well as by primary MedDRA SOC and Preferred Term. The SOCs will be presented in alphabetical order, and the PTs will be presented in descending percentage in atogepant 60 mg QD group within each SOC.

The number and percentage of participants experiencing treatment-emergent AEs will be summarized.

TEAEs that started after the date of last dose of study treatment will be considered as newly emergent. The number and percentage of participants reporting newly emergent TEAEs in each treatment group will be summarized by system organ class and preferred term for participants who entered the safety follow-up period.

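### SAP 10.2 specifies only the follow-up half of the by-phase AE summary in Protocol 9.4.2.1, so the main TEAE percentages pool unequal observation windows that depend on rollover

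*SAP*

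**What the plan says.** SAP 2.2 describes the schedule: "The double-blind treatment period will last 12 weeks, with a subsequent safety follow-up period of 4 additional weeks". It adds: "Total duration of study participation for one participant is approximately 20 weeks". On follow-up it says: "The Visit 8/EOS/follow-up period must be completed for all participants who take at least one dose of study intervention, except for participants rolling over" into the extension, Study 3101-312-002. It continues: "For these rollover participants Visit 8 is not required, because the final Follow-up Visit will be performed" when the extension ends.

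SAP 10.2.1 sets the outer limit for TEAEs: "An AE that occurs more than 30 days after the last dose of double-blind study treatment or Visit 8 whichever comes later" is not counted. Protocol 9.4.2.1 has the same limit. SAP 10.2 then confines this study's TEAEs to events captured in this study. For rollover participants, "AEs captured in the extension study will be summarized in the extension Study 3101-312-002 although some AEs might occur within 30 days" of the last dose in this study.

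Protocol 9.4.2.1 also states: "AEs will also be summarized separately for the double-blind treatment and safety follow up phases of the study". The SAP's only by-phase AE table is the newly emergent one in 10.2.1, which covers TEAEs with onset after the date of last dose among participants who entered follow-up. The overview, SOC/PT, severity, relationship, 2%, 5% and TESAE tables in 10.2.1 to 10.2.4 carry no phase restriction. SAP 15.1 lists two changes from the protocol, the 14-day diary rule and the subgroups. Neither concerns AEs.

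**The concern.** Participants with different lengths of AE observation enter the same numerators and denominators, and the length depends partly on rollover. Rollover is decided after randomisation and may be related to benefit or tolerability, so it could differ between arms. The arm with less rollover would be watched longer on average and would show more participants with at least one event, even with no drug effect.

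The by-phase summary in the protocol would let a reader see the on-treatment comparison without that component, but the SAP does not specify it. It cannot be recovered by subtracting the newly emergent table from the full-window table, because one participant can have events in both periods and the denominators differ. No exposure-adjusted AE rate is planned either, and the participant-years in SAP 6.0 measure time on treatment, not time under AE observation.

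**Working it through.** **Windows.** The plan's total reproduces: 4 weeks of baseline + 12 + 4 = 20 weeks. The Schedule of Activities in Protocol 1.3 puts Visit 7 at Day 84 and Visit 8 at Day 112. Protocol Section 7 puts Visit 8 four weeks after the last dose for those who stop early.

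| Group | AE observation in this study, from first dose |
|---|---|
| Rollover completer | about 84 days |
| Non-rollover completer | about 112 days (112/84 = 1.33, or 33% longer) |
| Early terminator | time on drug + about 28 days |

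**Size of the artefact.** The documents give neither rollover rates nor expected TEAE rates, so these are assumptions: 12-week incidence p12 of 50% for any TEAE and 5% for a single preferred term; completers only; no true drug effect; constant hazard, with a variant that halves it in follow-up.

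Let r be the rollover share in an arm and p16 the 16-week incidence. Crude incidence = r × p12 + (1 − r) × p16. The between-arm artefact is therefore the rollover gap × (p16 − p12).

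- Any TEAE, full hazard: h = ln 2 / 12 = 0.0578 per week. p16 = 1 − exp(−16h) = 60.3%, which is 10.3 points extra.
- Any TEAE, half hazard in Weeks 13 to 16: 1 − exp(−14h) = 55.5%, which is about 5.5 points extra.
- 5% term, full hazard: p16 = 1 − 0.95^(112/84) = 6.6%, which is 1.6 points extra.

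| Rollover gap | Any TEAE, full hazard | Any TEAE, half hazard | 5% term, full hazard |
|---|---|---|---|
| 0 points | 0 | 0 | 0 |
| 10 points | 1.0 | 0.55 | 0.2 |
| 20 points | 2.1 | 1.1 | 0.3 |
| 40 points (extreme) | 4.1 | 2.2 | 0.6 |

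Entries are percentage points, higher in the arm with less rollover. Counting 30 days of follow-up instead of 28 moves the 2.1 to 2.2.

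**With a true difference.** Take 55% versus 50% at Week 12, a difference of +5.0, with the same constant-hazard model. Rollover of 80% (atogepant) and 60% (placebo) shows +3.0. The reverse, 60% and 80%, shows +7.1. Equal rollover of 70% shows +5.1.

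**Feasibility.** The SAP already splits by period elsewhere: C-SSRS in 10.5.2, and in 7.3 a table of concomitant medications used by at least 5% of participants in the double-blind period. The cut-point needed for AEs, the date of last dose, is already in 10.2.1.

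**The case against.** The strongest reply has four parts.

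1. **The wide window comes from the protocol.** Protocol 9.4.2.1 itself runs TEAEs to the later of 30 days after last dose or Visit 8, and its by-phase summary is additional. This stands. A reader might infer that the SAP departed from the protocol's main TEAE definition, or that honouring the protocol means making the double-blind table primary. Neither follows; the departure is the missing table.

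2. **Silence is not removal.** SAP 1.0 places table specifications in separate documents, so a double-blind AE table may exist there, and all AEs are listed by participant. This also stands. The SAP text shows an omission, not a decision. But the SAP is where the analysis is pre-specified, and it spells out the follow-up half only.

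3. **The effect is small and conditional.** With 150 per arm and 50% incidence, the standard error of a difference is sqrt(2 × 0.25 / 150) = 5.8 points, so 0.55 to 2.1 points is about 0.1 to 0.4 of a standard error. The AE results are descriptive. Amendment 2's stated reason for dropping the Week 16 HIT-6 and MSQ endpoints predicts that many participants will enter the extension and few will have Visit 8, and high rollover in both arms would limit the gap. This stands on size. It does not remove the mismatch between the documents.

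4. **A double-blind table does not equalise observation.** If discontinuation differs by arm, so does time on treatment. This is correct: the table removes the part that depends on rollover and nothing more.

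It is also tempting to describe those who do not roll over as people unwilling to continue. The documents give no reasons for non-rollover, and Protocol 4.1 and SAP 2.2 include participants who fail screening for the extension. Even the direction of any bias is unknown.

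**Conclusion.** The protocol-SAP mismatch holds whatever the rollover rates: half of the by-phase AE summary is unspecified and SAP 15.1 does not say so. As written, the main TEAE percentages depend on rollover, and their between-arm difference carries an observation-time component only if rollover differs by arm. Under assumed gaps of 10 to 20 points, 50% incidence at Week 12 and full or half follow-up hazard, that component is about 0.55 to 2.1 points for any TEAE. For a 5% preferred term at full hazard it is about 0.2 to 0.3 points. With no drug effect and equal rollover it is zero. The full-hazard figures probably sit at the high end, since AE rates off treatment are usually lower.

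A reader might infer that the safety comparison in this trial is biased, or that all participants outside the rollover group are observed for 16 weeks. The documents support neither. They give no rollover rates by arm, and 16 weeks applies only to completers who do not roll over. This is worth correcting because the correction is cheap, not because the distortion is large.

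**What to change.** In SAP 10.2.1 to 10.2.4, add TEAE, TESAE and common-TEAE (2% and 5%) tables by arm for all Safety Population participants, restricted to onset from first dose through the date of last dose of double-blind treatment. Within TEAEs this is the exact complement of the newly emergent definition, so no event falls in both. A window ending at Visit 7/ET should be avoided, because an event between the last dose and that visit would be counted in both tables.

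Keep the full-window and newly emergent tables. There is no need to change which table is primary.

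Report rollover by arm beside the AE tables, counting participants who actually entered the extension. SAP 5.0 counts those who signed extension consent, and a consenter who then fails screening still has Visit 8.

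If the sponsor prefers not to add the tables, SAP 15.1 should declare and justify the departure from Protocol 9.4.2.1.

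Cost: one period flag and one extra set of tables, with no new data. The downside is longer output.

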### **10.2.1 Treatment-Emergent Adverse Events**

Treatment-emergent AEs are defined as any AE with the onset that is after the first dose of study drug. Events when the onset date is the same as the study drug start date are assumed to be treatment-emergent. An AE that occurs more than 30 days after the last dose of double-blind study treatment or Visit 8 whichever comes later will not be counted as a TEAE. All treatment-emergent AEs will be summarized overall, as well as by primary MedDRA SOC and Preferred Term. The SOCs will be presented in alphabetical order, and the PTs will be presented in descending percentage in atogepant 60 mg QD group within each SOC.

The number and percentage of participants experiencing treatment-emergent AEs will be summarized.

TEAEs that started after the date of last dose of study treatment will be considered as newly emergent. The number and percentage of participants reporting newly emergent TEAEs in each treatment group will be summarized by system organ class and preferred term for participants who entered the safety follow-up period.

### **10.2.2 Adverse Event Overview**

An overall of AEs will be presented consisting of the number and percentage of participants experiencing at least one event for each of the following AE categories.

- Any treatment-emergent SAEs
- Any treatment-emergent AEs related to study drug according to the investigator
- Any serious treatment-emergent AEs
- Any treatment-emergent AEs leading to discontinuation of study drug

- All deaths

### **10.2.3 Treatment-Emergent Adverse Events by SOC and/or PT**

Treatment-emergent adverse events will be summarized by SOC and PT; by maximum relationship to study drug as assessed by the investigator (e.g., reasonable possibility or no reasonable possibility) and SOC and PT; and by maximum severity and SOC and PT. Specific adverse events will be counted once for each participant for calculating percentages, unless stated otherwise. In addition, if the same adverse event occurs multiple times within a participant, the highest severity and level of relationship to investigational product will be reported.

The incidence of common ( $\geq 2\%$  of participants [after rounding] in any treatment group) TEAEs will be summarized by preferred term, and treatment group. A similar 5% table will be provided as well.

### **10.2.4 Deaths, Serious Adverse Events, and Adverse Events Leading to Study Treatment Discontinuation**

An AE will be considered a treatment-emergent serious adverse event (TESAE) if it is a TEAE that additionally meets any SAE criterion. TESAEs, TEAEs leading to premature discontinuation of study treatment, and TEAEs leading to death will be summarized by SOC and PT. Tabular listings will be provided for all AEs, all deaths, all SAEs, and TEAEs leading to premature discontinuation of study treatment.

### **10.2.5 Adverse Events of Special Interest**

An adverse event of special interest (serious or nonserious) is one of scientific and medical concern specific to the sponsor's study intervention or program, which warrants ongoing monitoring and rapid communication by the investigator to the sponsor. Such an event might warrant further investigation in order to characterize and understand it.

The following AESI(s) have been identified for the study intervention(s):

- Treatment-emergent suicidal ideations with intent, with or without a plan, (i.e., Type 4 or 5 on the C-SSRS) or any suicidal behaviors.
- Treatment-emergent elevated ALT or AST laboratory value  $\geq 3 \times \text{ULN}$ .
- Potential Hy's law cases: elevated ALT or AST laboratory value that is  $\geq 3 \times \text{ULN}$  and an elevated total bilirubin laboratory value that is  $\geq 2 \times \text{ULN}$  and, at the same time, an alkaline phosphatase laboratory value that is  $< 2 \times \text{ULN}$ .

AESIs will be summarized. Listing of AESIs will be provided.

